## Presumed Phospholipidosis (PLD):

In the 28 day studies in both rats and monkeys, foamy macrophages and vacuolated infiltrates were found in multiple organs and various tissues, and presumed to be signs of PLD. PLD can only be confirmed with electron microscopy which was not done in the 28 day study. In most tissues, these infiltrates did not appear to be adverse and there were no clinical or blood chemistry findings that correlated. Importantly, the infiltrates were fully or partially reversible in both species. The partial reversibility in monkeys may have been due to the continued presence of BCX7353 in plasma even at Day 50 of the 28-day dosing study.

In the 13-week studies in rats, the liver showed vacuolated macrophages with electron microscopic features consistent with PLD. In the monkey 13-week study there were no microscopic abnormalities, and no foamy macrophages or vacuolated cellular infiltrates were observed. Increased urinary levels of di-docosahexaenoyl (22:6)-Bis(mono)acylglycerol phosphate (BMP), an investigational biomarker for PLD, were demonstrated in both rats and monkeys dosed with BCX7353 for 13 weeks. This increase was dose related and reversible upon cessation of BCX7353 in both species. These data suggest that the urinary BMP changes induced by BCX7353 in both rats and monkeys may not be associated with PLD, given the differences seen microscopically between the two species.

PLD is not adverse in and of itself and there are many approved products that cause this phenomenon without any unmanageable toxicities. Since PLD requires accumulation of drug, it is highly unlikely that subjects are at any risk of this phenomenon with individual doses of study drug, separated by at least 14 days at a minimum. The primary method of ensuring subject safety will be to monitor organ toxicity and subject well-being through adverse event reporting and vital signs including weight. Since phospholipidosis is not toxic in and of itself, organ health including function and signs of inflammation will be monitored. Monitoring of renal, liver, cardiac, and muscle health will be achieved with routine safety assessments, including ECGs.

Gastrointestinal (GI) symptoms: Gastrointestinal symptoms, all mild, were noted in half of the subjects receiving a single 1000 mg single dose in the Phase 1 BCX7353-101 study. The events were both upper GI (nausea, dyspepsia, and vomiting) and lower GI (diarrhea). The events resolved without treatment. No pertinent GI events occurred in the 500 mg single dose cohort but 2 subjects reported GI symptoms at 100 mg. During multiple day dosing (part 2), all cohorts experienced GI symptoms when BCX7353 was given over 7 to 14 days. Symptoms were primarily lower gastrointestinal (diarrhea and flatulence) at 500 mg QD × 7 days and primarily upper gastrointestinal (abdominal pain, dyspepsia) at 350 mg QD × 14 days without any pertinent laboratory or physical exam findings. In the Japanese 250 mg × 7-day cohort, a single subject had abdominal pain. All subjects reporting these events took study drug in a fasting state. Two subjects discontinued study drug, one after a single 500-mg dose of BCX7353 due to diarrhea and abdominal pain, and one after 10 days of 350 mg BCX7353 due to abdominal pain. Neither subject had any clinically significant laboratory abnormalities. The Phase 1 study demonstrated no adverse impact on the extent of drug exposure from taking BCX7353 with food in 6 subjects who received a dose of BCX7353 (250 mg) under fed and fasting conditions. However, the time to achieve maximal blood concentrations was delayed when BCX7353 was administered with food (median Tmax increased from 2 to 5 hours, with 4 of 6 subjects experiencing a delay in Tmax with food relative to fasting). Therefore, since food may materially delay achievement of effective blood levels and the gastrointestinal effects to date have been a

tolerability issue but not a safety issue, BCX7353 is recommended to be taken without food and to delay food at least one hour (to allow for gastric emptying). However, due to the unpredictability of onset and location of HAE attacks, recent food intake will not necessarily prohibit an attack from being approved for treatment with study drug in this study. The time of the last meal prior to the attack will be captured to assess whether recent food ingestion prior to an attack may affect efficacy.

Subject well-being with respect to possible gastrointestinal symptoms will be monitored through adverse event reporting and laboratory assessment.

Drug rash: A benign maculopapular exanthema consistent with a delayed type drug rash has been seen in 3 subjects taking multiple doses of BCX7353 to date. In Studies BCX7353-101 and BCX7353-102, a total population of BCX7353 exposed subjects who have received at least 7 days of BCX7353 doses is 68, equating to an incidence rate of 4.4%. In all cases, symptoms were observed or reported approximately 2 days after daily BCX7353 dosing ended: one subject who completed 500 mg QD BCX7353 x 7 days (Study BCX7353-101), one subject of Japanese heritage who completed 250 mg QD BCX7353 x 7 days (Study BCX7353-101), and one subject who recently completed 9 days of BCX7353 350 mg QD (Study BCX7353-102). In all cases, no systemic or constitutional symptoms, no organ involvement, no desquamation or mucosal involvement was observed, no clinically significant laboratory abnormities were present and the rash rapidly resolved. Two subjects received an oral antihistamine and 1 subject received oral and topical steroids.

Hypersensitivity is a risk with any drug. In all three cases, the rashes have been limited and resolved quickly. Subjects should report any rashes, pruritus, or skin changes. Evaluation of any suspected drug-induced rash will be required with high resolution photography and clinical laboratory assessments in order to better define this risk; skin biopsy of a fresh lesion should be obtained for histopathologic examination, where possible. The management of rash is specifically addressed in Section 11.1.11. It is unknown if repeat exposure of single doses will result in hypersensitivity.

### **5.4.5.** Benefits of Trial Participation

Study subjects will receive regular medical care for the duration of the study. Subjects may experience a resolution in their acute attacks after receiving active study drug; however, subjects will be blinded to their treatment sequence so they will not know if they are receiving BCX7353 or placebo for any given treated attack.

The development of BCX7353 may be of benefit to the wider community/patients with HAE.

#### 5.4.6. Overall Benefit-Risk Assessment

The risks seen to date in both preclinical and clinical studies at the study doses were primarily mild, monitorable, and reversible. Although there may be no direct benefit to any individual subject, the information obtained from this study will support the development of BCX7353 for treatment of acute attacks in patients with HAE, a life-threatening disease. The overall risk benefit balance is therefore considered to be acceptable.

# 6. TRIAL OBJECTIVES AND PURPOSE

# 6.1. Objectives

The primary objective of this study is as follows:

• To evaluate the efficacy of single oral doses of BCX7353 in treating acute attacks in subjects with HAE

The secondary objectives of this study are as follows:

- To evaluate the safety and tolerability of single oral doses of BCX7353 in subjects with HAE
- To evaluate the relationship of BCX7353 dose with clinical responses
- To evaluate subject satisfaction with BCX7353 treatment
- Substudy: to describe the natural history and temporal pattern of symptoms of untreated attacks and those treated with commercially available attack medications

#### 7. INVESTIGATIONAL PLAN

# 7.1. Overall Study Design

This is a 3-part, Phase 2, randomized, double-blind, placebo-controlled, dose-ranging study to evaluate the efficacy and safety of single oral doses of a liquid formulation of BCX7353 in the treatment of acute HAE attacks. All subjects enrolled will receive both active and placebo blinded study drug in a randomized sequence. Part 1 of the study will evaluate single doses of BCX7353 750 mg; Part 2 will evaluate single doses of BCX7353 500 mg and Part 3 will evaluate single doses of BCX7353 250 mg.

HAE patients with a documented recent history of angioedema attacks who have provided written informed consent will be evaluated for participation in this study at a screening visit.

Up to 36 subjects with Type 1 or 2 HAE with a documented history of HAE attacks will be sequentially enrolled into Part 1 of the study and randomized to a treatment sequence containing the following:

- Treatment A: Single oral dose of BCX7353 750 mg
- Treatment B: Single oral dose of placebo

Note: Treatment  $A^1$  = single oral doses of BCX7353 750 mg in Part 1; Treatment  $A^2$  = single oral doses of BCX7353 500 mg in Part 2; or Treatment  $A^3$  = single oral doses of BCX7353 250 mg in Part 3.

Initially in Part 1, 12 subjects will be randomized 1:1:1 to 1 of 3 treatment sequences (n = 4 subjects per treatment sequence):

- Sequence 1:  $A \rightarrow B \rightarrow A$
- Sequence 2:  $B \rightarrow A \rightarrow A$
- Sequence 3:  $A \rightarrow A \rightarrow B$

Both subjects and site staff will be blinded to which treatment sequence a subject is randomized to receive.

[figure not shown]
If required, additional subjects will be enrolled into Part 1 (see below) using the same 1:1:1 ratio for the 3 treatment sequences, with a maximum total number of 36 subjects for Part 1.

Part 2 will evaluate a dose of 500 mg (Treatment  $A^2$ ) and placebo (Treatment B). A maximum of 12 subjects will be enrolled, using the same 1:1:1 ratio for the 3 sequences. Part 3 will evaluate a dose of 250 mg (Treatment  $A^3$ ) and will enroll a maximum of 12 subjects in a 1:1:1 ratio for each of the 3 treatment sequences.

If tolerability issues prevent enrollment of Part 1 as described, additional subjects in Part 1 may be dosed with active study drug at a dose of 500 mg. If the Part 1 dose is reduced and at least 12 subjects are treated with an active study drug dose of 500 mg, a 250 mg active dose may be assessed in Part 2. Any further dose level changes warranted for Part 2 and Part 3 will be instituted via a protocol amendment.

The overall study design is presented in Figure 2.

Figure 2. Study Design Through Follow-up (Post-Attack 3 Visit)

#### 7.1.1. Enrollment and Analyses

Up to 36 subjects will be enrolled in Part 1. Upon full enrollment, enrollment into Part 2 of the study (maximum of 12 subjects) may immediately commence. Likewise, Part 3 (n = up to 12) may immediately commence upon enrollment of Part 2.

Following the 12th subject completing Part 1, the treatment effect may be estimated. The predefined endpoint, determined by the Haybittle-Peto method, is the proportion of subjects with a stable or improved composite VAS at 4 hours postdose of an HAE attack. A Haybittle-Peto boundary of p < 0.001 is considered clinically significant.

If the Haybittle-Peto analysis is run and the boundary is not crossed with 12 subjects, the treatment effect may be re-estimated with cumulative data after each treated attack in accordance with the fully sequential analysis method. At each evaluation, the treatment effect may be assessed using the Haybittle-Peto boundary (p < 0.001).

Alternatively, if the boundary is not crossed with 24 subjects enrolled or the Heybittle-Peto analyses are not performed, treatment differences may be assessed using available data in Parts 1, 2 and 3 in order to plan subsequent studies.

## 7.1.2. Study Conduct Overview

At the Screening visit, potential subjects will be given a diary and receive instruction on the correct completion of the diary in real-time to record attack symptoms and severity and any medication usage during an attack. During the 35-day screening period, subjects will be required to: 1) phone the on-call Investigator (or designee) at the onset of pain or swelling associated with an HAE attack; 2) complete details in real time of this HAE attack; and 3) phone the on-call Investigator (or designee) again in at least 4 hours time. Completion of these procedures will confirm that the subject is able and competent to perform on-study requirements in early identification of an attack and treating and documenting an HAE attack.

Eligible subjects will return to the clinic to attend a Baseline visit. At the conclusion of the Baseline visit, subjects will receive their first (single) randomized dose of study drug for treatment of attacks by self-administration. The IMP is supplied as a powder form of drug in a bottle that will require reconstitution to a liquid formulation with vehicle, by the subject, prior to self-administration.

At the Baseline visit, all subjects will be instructed on how to prepare and use study drug to treat a protocol-qualified HAE attack and will receive further instruction on the correct completion of a diary in real-time immediately prior to and after study drug administration.

Specifically, subjects will be instructed with respect to treatment of attacks with study drug by self-administration as follows:

1. At the first symptom of swelling or pain known to be associated with a potentially protocol-qualified attack, the subject will phone their on-call study Investigator (or designee) who will review the subject's symptoms by phone. The Investigator will confirm that their symptoms constitute an acute attack that qualifies for treatment with study drug.

Protocol-qualified attacks approved for study drug treatment must meet all of the following:

- have pain and/or swelling associated with an HAE attack reported as a symptom
- subject has contacted Investigator within approximately 1 hour of onset time of HAE pain and/or swelling
- not involve pain or swelling in the throat or mouth. Such attacks should be treated using the subject's standard of care acute attack treatment (e.g., C1 INH, icatibant) without delay.
- not be an abdominal attack that has already resulted in vomiting. Such attacks should be treated using the subject's standard of care acute attack treatment (e.g., C1 INH, icatibant).
- have an identifiable onset time, with the exception that abdominal attacks with an
  onset during sleep may be permitted for study drug treatment. Onset time for
  abdominal attacks will be time the subject woke up with symptoms. Peripheral
  attacks starting with an onset during sleep will not be approvable for study drug
  treatment.
- occur during an HAE symptom-free period as follows:
  - o if the previous HAE attack was treated with a bradykinin B2 receptor antagonist (i.e. Firazyr) OR treated with human recombinant C1 INH (i.e. Ruconest) OR any non-targeted therapy (i.e. pain medication, anti-spasmodic, anti-emetic, tranexamic acid) OR was not treated with any medication: new attack can be treated with IMP if has been 48 hours since the complete resolution of all symptoms of the previous HAE attack AND the Investigator believes it is a new (de novo) attack.

OR

- if the previous HAE attack was treated with plasma-derived purified C1 INH
   (i.e. Berinert or Cinryze) OR plasma preparation (fresh frozen or solvent
   detergent plasma): new attack can be treated with IMP if it has been 96 hours
   since the complete resolution of all symptoms of the previous HAE attack
- occur at least 96 hours after complete recovery from a procedure or injury

- occur at least 14 days from a previous dose of study drug
- 2. Only after receiving confirmation by the on-call Investigator (or designee) should a subject reconstitute study drug with vehicle and take it to treat the HAE attack. Reconstitution and ingestion of the study drug should occur almost immediately (within 5 minutes) following the phone call, with the goal for subjects to take study drug within approximately one hour of the onset of symptoms.
- 3. At 4 hours post study drug intake, subjects who are not experiencing improvement or who are experiencing progression of the HAE attack can use their standard of care acute attack treatment, if warranted. However, if the subject feels that an attack is progressing rapidly after administration of study drug or intraoral symptoms develop, the subject may treat the attack with their standard of care attack medication prior to 4 hours.
- 4. The subject will call the on-call study Investigator (or designee) at least 4 hours after taking study medication (or earlier if they have any concerns over the course of their symptoms) to review their response to study drug and diary completion. The on-call study Investigator (or designee) will call the subject if they have not heard from the subject within 5 hours of their initial phone call. Subjects who did not require standard of care at 4 hours will be reminded at the telephone call, by the Investigator, that they may use standard of care at any time point at their own discretion if not experiencing improvement or if they are experiencing progression of the HAE attack. An exception to the requirement of a phone call follow-up at 4 hours may be made if the 4 hour timepoint occurs during the typical period of sleep and the subject is asleep at 4 hours post-study medication. In this case, the subject will be required to call the on-call Investigator (or designee) upon waking.

Subjects will complete a diary questionnaire and a 3-component VAS on a 100 mm scale for abdominal pain, cutaneous pain, and cutaneous swelling immediately prior to study drug administration and at 1, 2, 3, 4, approximately 8 and at 24 hours after study drug administration. Subjects sleeping during these timepoints (see #4 exception above) will be required to complete the diary questionnaire upon waking. Subjects will also be asked to track the start and stop times of any attacks not treated with study drug that occur after the baseline visit through the last study visit (Post-Attack 3 visit).

At each clinic visit following treatment of an attack with study drug, the diary will be reviewed. Any re-education required to ensure correct diary completion will be performed and safety assessments will be completed. At Post-Attack 1 and Post-Attack 2 clinic visits, the subject will be dispensed their next randomized dose of study drug and a new attack diary. Completed diaries will be collected at each visit to avoid subjects referencing back to previous attack entries.

Each subject will continue on study to treat 3 protocol-qualifying attacks with study drug. Clinic visits will be scheduled 10 to 14 days after each attack that is treated with study drug. Any additional attacks that occur in the intervening periods between study visits may be treated according to standard of care for the subject.

Sites must attempt to contact subjects every 7 days from the last clinic visit to inquire about the occurrence of an attack if the subject has not contacted the site during this timeframe.

Subjects will be asked to participate in an optional observational substudy to obtain diary data on all HAE attacks, commencing from the Post-Attack 3 visit. Consenting subjects will receive a diary and instruction for completion at the Post-Attack 3 visit. For the next 12 weeks, subjects will complete diaries provided on an as-needed basis with periodic subject contact to ensure adherence with diary completion.

## 7.2. Endpoints

# 7.2.1. Efficacy Endpoints

The efficacy endpoints of this study are as follows:

- Proportion of subject attacks with an improved or stable 3-symptom composite VAS score at 4 hours post-dose. The 3-symptom composite will be calculated as the average of the VAS scores for abdominal pain, skin pain, and skin swelling. A subject is considered improved or stable if the change from baseline (time of drug administration) in VAS is less than or equal to 0
- Proportion of subject attacks with a patient global assessment of improved or stable symptoms at 4 hours post-dose
- Proportion of subject attacks with no symptoms or mild symptoms of an HAE attack at 4 hours post-dose
- Proportion of subject attacks requiring standard of care attack treatment through 24 hours post-dose
- Time to use of standard of care acute attack treatment through 24 hours post-dose
- Time to stable or improved symptoms by composite VAS score through 24 hours post-dose
- Time to symptom relief (first documented time point when a subject experiences a 50% reduction in the 3-symptom composite VAS from the pretreatment composite score)
- Time to almost complete symptom relief (first documented time point when a subject records a VAS score < 10 mm in the 3-symptom composite VAS score)
- Time to initial symptom relief (time from ingestion of study medication to report that the worst symptoms of the attack are over)
- Time to complete symptom relief (time from ingestion of study medication to no HAE attack symptoms)

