#### Selection of duration that BCX7353 concentrations must exceed the target plasma level

To abate an attack, it is desirable to exceed the target plasma concentrations of BCX7353 as quickly as possible after a dose. HAE attacks typically follow a predictable time course. Swelling classically worsens slowly but relentlessly over the first 24 hours, and gradually subsides over the subsequent 48 to 72 hours. Following administration of a single dose formulated in a capsule in Study BCX7353-101, BCX7353 was rapidly absorbed. Mean plasma concentrations exceeded 71 ng/mL by 0.5 to 1 hour postdose at doses ranging from 250 to 1000 mg. Administration of a

liquid formulation in the current study is expected to achieve target levels earlier. In summary, target concentrations of BCX7353 are achievable early in the development of an HAE attack.

Current treatments for acute attacks of angioedema in HAE patients are administered parenterally, and sometimes retreatment is required after a period to time due to a lack of symptom relief. The label for Firazyr (icatibant) specifies that patients should administer additional doses every 6 hours if symptoms have not improved, and analysis of the open-label extension period of FAST-1 showed that 11.8% of treated attacks required more than one injection of Firazyr (icatibant) (Malbran, Riedl et al. 2014). The need for redosing could indicate that adequate plasma concentrations of icatibant are not of a sufficient duration to alleviate the symptoms of the attack or that a rebound effect is occurring. For an acute treatment, it would be advantageous to rapidly achieve plasma concentrations of BCX7353 at levels that lead to potent inhibition of plasma kallikrein, and maintain these concentrations above this level for longer than 6 hours.

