#### 11.2.2. HAE Attack Diaries and Phone Calls

## 11.2.2.1. Screening through Post-Attack 3 Visit

The Sponsor will supply an attack diary for subject documentation of one HAE attack occurring during the screening period and for each of 3 study-drug treated attacks. To ensure compliance with on-study requirements in treating an appropriate attack with study drug after the Baseline visit, subjects will be required to complete timed attack details of at least 1 HAE attack during the screening period after approval of the on-call Investigator (or designee). Subjects will also be required to complete the details of three HAE attacks that are treated with study drug, each after approval from the on-call Investigator (or designee).

All attacks for which acute attack diaries are completed by the subject will be included in the eCRF.

Apart from the principal Investigator at each clinical site, the Sponsor will approve on-call study Investigators (or designees). Approval will be based upon demonstration that the proposed on-call Investigator (or designee) ordinarily has oversight of the care of HAE patients.

The diaries will be composed of a questionnaire and 3-component VAS on a 100 mm scale for abdominal pain, cutaneous pain, and cutaneous swelling. The questionnaire includes queries about symptom location, severity/limitation of activities and a global assessment that qualitatively compares HAE symptomatology against that experienced prior to study drug intake. The diaries will include questions/VAS to be completed prior to study drug administration and 1, 2, 3, 4, approximately 8 and at 24 hours post study drug intake (or post call for a screening attack). All medications used from the time of symptom onset through 24 hours postdose will also be captured in the diary, including standard of care treatment for acute attacks and any symptomatic treatments such as analgesics.

At the Screening, Baseline, and Post-Attack 1 and Post-Attack 2 visits, attack diaries will be dispensed and the subject will be instructed on completing the diary (written instructions may also be provided). In addition, subjects will be informed of what is expected regarding attacks likely to be approved for study drug treatment by the Investigator and also administration of standard of care rescue medication on a continuing basis.

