# 13.3.3. Analysis of Efficacy Variables

As this is the first study of BCX7353 in the treatment of acute attacks, the analysis of attack resolution will be described in a number of ways which will be fully detailed in the SAP. The endpoint that may be utilized to first examine efficacy is the proportion of subject attacks with a stable or improved VAS at 4 hours postdose in the full analysis set. The number and proportion of subject attacks with a stable or improved VAS at 4 hours postdose will be summarized by treatment group. Attacks that require standard of care medication prior to the 4 hour time point will be considered as failure (i.e., not having a stable or improved VAS at 4 hours postdose). To assess treatment differences, a logistic mixed effect model including treatment, period and sequence as fixed effects, and subject within sequence as a random effect will be utilized. Other binary endpoints will be analyzed in a similar manner.

The 3-symptom composite VAS and its associated changes from baseline will be summarized for each attack by time point and treatment group. Treatment differences in the change from baseline values at each time point will be assessed with a mixed effect linear model with factors for treatment, period, sequence, and baseline value as fixed effects, and subject within sequence as a random effect. Analyses of other continuous variables will be analyzed in a similar manner.

The time to use of standard of care medication will be estimated using the method of Kaplan-Meier. For each attack, subjects who do not use standard of care medication will be censored at the end of the attack observation period (i.e., 24 hours). Treatment differences will be assessed using an appropriate proportional hazards model. Analyses of other type to event variables will be analyzed in a similar manner.

Location of attacks, duration of attacks, and number of acute HAE medications administered will be summarized for each treatment group.

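### The 4-hour no-or-mild endpoint ignores severity at dosing and its model has no pre-dose term, which costs precision and clarity but does not bias the randomised comparison

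*Protocol*

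**What the plan says.** **Endpoint.** Protocol 7.2.1 lists ten efficacy endpoints. The third is the "Proportion of subject attacks with no symptoms or mild symptoms of an HAE attack at 4 hours post-dose", and nothing in it refers to the state before dosing. The other two 4-hour responder endpoints do look back: the VAS responder is defined on change from baseline, and the global assessment compares with symptoms before study drug (11.2.2.1).

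**Entry.** Under Protocol 7.1.2 the subject telephones "At the first symptom of swelling or pain known to be associated with a potentially protocol-qualified attack" and doses soon after approval, "with the goal for subjects to take study drug within approximately one hour of the onset of symptoms". The attack must "have pain and/or swelling associated with an HAE attack reported as a symptom", and a further condition is that the "subject has contacted Investigator within approximately 1 hour of onset time of HAE pain and/or swelling". The remaining conditions concern site, vomiting, onset time and the interval since earlier attacks, procedures or doses. None sets a minimum severity.

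**Analysis.** For the 4-hour VAS responder, Protocol 13.3.3 states that "a logistic mixed effect model including treatment, period and sequence as fixed effects, and subject within sequence as a random effect will be utilized", and it treats the other binary endpoints likewise. The next paragraph gives the continuous VAS model a baseline term.

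**Data.** Protocol 11.2.2.1 states: "The diaries will include questions/VAS to be completed prior to study drug administration". The questionnaire in that diary asks about severity.

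**SAP.** The SAP supplied belongs to study BCX7353-302 (SAP section 2) and does not cover this endpoint.

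**The concern.** With dosing in about the first hour and no severity floor, mild is a natural state in which to enter. The endpoint then counts mild as success. A mild attack succeeds by not changing, whereas a moderate one succeeds only by improving. Pre-dose severity is therefore likely to be a strong predictor of the outcome, and the model leaves it out.

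The subject random effect absorbs stable differences between subjects. It does not absorb differences in starting severity between one subject's attacks, and the treatment contrast is made between those attacks.

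Two things are at stake. One is precision, in a trial sized without a power calculation (Protocol 13.1). The other is meaning: a response rate that pools attacks that stayed mild with attacks that became mild does not show which of the two the drug affected.

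**Working it through.** **Nothing to reproduce.** The protocol gives no event rate, sample size or power for this endpoint. The power figure in the supplied SAP is for study 302 and plays no part here.

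**Inputs from the protocol.** Each subject contributes two active attacks and one placebo attack (9.1). The first Part 1 cohort has 12 subjects, giving 24 active and 12 placebo attacks. The Part 1 maximum of 36 subjects gives 72 and 36 (7.1).

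**Assumed inputs.** The documents give no severity mix. The central case takes a share mild at dosing of p = 0.50, and 4-hour response without drug effect of 0.60 if mild and 0.10 if worse. Attacks are treated as independent.

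**Step 1: who the responders are with no drug effect.**
- Response rate = 0.50 × 0.60 + 0.50 × 0.10 = 0.35.
- Share of responders already mild at dosing = 0.30 / 0.35 = 86%.
- With p from 0.4 to 0.8 and 40 to 80% of mild attacks remaining responders, the rate runs from 0.4 × 0.4 + 0.6 × 0.1 = 0.22 to 0.8 × 0.8 + 0.2 × 0.1 = 0.66. The share runs from 0.16 / 0.22 = 73% to 0.64 / 0.66 = 97%.

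**Step 2: contribution of chance severity imbalance, set against the whole standard error.**
- SD of the difference in share mild = √[p(1 − p)(1/nA + 1/nP)]. Multiply by the response gap (0.60 − 0.10 = 0.50).
- Total SE of the response difference = √[0.35 × 0.65 × (1/nA + 1/nP)].

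| Subjects | 1/nA + 1/nP | SD of share mild | Contribution (× 0.50) | Total SE |
|---|---|---|---|---|
| 12 | 0.1250 | 17.7 points | 8.8 points | 16.9 points |
| 36 | 0.0417 | 10.2 points | 5.1 points | 9.7 points |

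The share of variance is the same at both sizes: (0.50² × 0.25) / (0.35 × 0.65) = 0.0625 / 0.2275 = 27%. With p = 0.50 and a response gap of 30 to 70 points, the contribution is 5.3 to 12.4 points at 12 subjects and 3.1 to 7.1 at 36.

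**Step 3: correlation within subject.** If severity has correlation ρ between one subject's attacks, the contribution shrinks by √(1 − ρ). At an assumed ρ of 0.5, 8.8 becomes 8.84 × 0.707 = 6.25 points and 5.1 becomes 5.10 × 0.707 = 3.6 points.

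**Step 4: error rate and power.** A simulation (200,000 runs, central case, two-sided 5% assumed) compared an unadjusted two-proportion test with a Mantel-Haenszel test stratified by pre-dose severity. It did not model subject, period or sequence.

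| | Unadjusted | Stratified |
|---|---|---|
| Type I error, 12 subjects | 5.3% | 4.8% |
| Type I error, 36 subjects | 5.3% | 5.0% |
| Power for a true 20-point effect, 12 subjects | 20% | 24% |
| Power for a true 20-point effect, 36 subjects | 50% | 63% |

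**The case against.** **Chance imbalance is not bias.** A reader might infer that it manufactures a drug effect. The documents do not support that. The trial is randomised and double-blind, so imbalance in starting severity is ordinary sampling error, already inside the standard error, and can hide an effect as easily as mimic one. The unadjusted test held its level in Step 4. A higher error appears only after conditioning on an unlucky draw. At 36 subjects, with active attacks 15 to 25 points more often mild, false findings in favour of the drug run at 12.1% against a nominal 2.5%. Near balance they run at 1.2%. This objection stands in full.

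**Staying mild may be the benefit sought.** Protocol 5.4.1.1 says: "Swelling classically worsens slowly but relentlessly over the first 24 hours, and gradually subsides over the subsequent 48 to 72 hours". On that course, an attack held mild at 4 hours may be a success, and the lead endpoint also credits stability. This stands as a reason to keep the endpoint. It is also a reason to report the two kinds of responder separately.

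**The severity mix is unknown.** That many attacks are mild at dosing is a reasonable inference from early dosing in a worsening course, but the protocol does not state it. The responder shares in Step 1 are conditional on assumptions.

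**The study's own SAP is not in hand.** Protocol 13.3 and 13.3.3 defer detail to a SAP, and treating other binary endpoints likewise does not forbid a baseline term. The omission is shown for the protocol only, not for the final analysis.

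**Low leverage and a small model.** This is one of ten endpoints in an exploratory study, and it is not the one carrying the Haybittle-Peto boundary. Twelve subjects give 36 attacks, and at 22% response about 8 responders. The fixed part already has six parameters (intercept 1, treatment 1, period 2, sequence 2). A strong seventh could cause separation or non-convergence. This stands and shapes the fix.

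**Conclusion.** The structural point holds on the text of the protocol: no severity floor at dosing, an absolute-state endpoint, and no pre-dose term in its model, although the neighbouring continuous model has one.

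The consequence is limited. The randomised comparison is not biased and its type I error is not inflated. Precision is lost, the realised estimate is open to severity imbalance in either direction, and two different kinds of responder are pooled. In the central case, pre-dose severity accounts for about 27% of the variance of the response difference: 8.8 of 16.9 points at 12 subjects and 5.1 of 9.7 at 36, as SD within SE.

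These sizes rest on an assumed severity mix, assumed response rates and independent attacks. The severity contribution is smaller if severity is correlated within subject. The change is worth making because it is cheap, not because the planned test is invalid.

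**What to change.** In Protocol 13.3.3, or in this study's own SAP, for this endpoint:

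1. Add pre-dose severity (mild or less against moderate or worse) as a fixed effect in the logistic mixed model. The diary form is not among the documents, so confirm that the severity item is asked before dosing in the same categories. The pre-dose composite VAS is an alternative that is certainly collected (7.1.2).
2. State in advance that the analysis falls back to the model without this term if the adjusted model does not converge or shows separation.
3. Tabulate 4-hour severity by pre-dose severity and treatment, so that attacks that stayed mild and attacks that became mild are shown separately.

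**Cost.** Some wording, one covariate and one table; study conduct does not change. The downsides are one more parameter in a small model and small table cells, most acutely at 12 subjects. The odds ratio also becomes conditional on pre-dose severity, so it should not be compared directly with an unadjusted one.
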